6.1.6. Leronlimab (PRO 140) - Disposition

All drug supplies are to be used only for this protocol and not for any other purpose. The investigator must not destroy any drug labels or any partially used or unused drug supply until instructed by the Sponsor. At the conclusion of the study and as appropriate during the course of the study, the investigator will return all used and unused drug containers and drug labels to the drug distributor as directed by the Sponsor. A copy of the completed drug disposition form will be sent to CytoDyn, Inc. or to its designee.

6.1.7. Leronlimab (PRO 140) - Accountability

Study drug must be used in accordance with this protocol and only under the direction of the responsible investigator. The investigational site must maintain complete and accurate records showing receipt and disposition of all study drug, including master records listing the date of receipt, the number and nature of medication units received, and a dispensing record which includes each quantity dispensed, identification of the staff member/subject to whom dispensed, the date of dispensing, the intended study participant, and the identification of the preparer. All used and unused study kits will be retained by the investigational site until drug accountability can be confirmed by study CRA during the monitoring visits. Instructions will be provided by Sponsor regarding final disposition of all study drug in compliance with applicable regulations.

6.2 CARBOPLATIN

6.2.1. Other names

CBDCA, Paraplatin, JM-8, NSC-241240

6.2.2. Classification – Type of agent

Second-generation tetravalent organic platinum compound

6.2.3. Carboplatin - Mode of Action

Like cisplatin, carboplatin binds to DNA, thereby inhibiting DNA synthesis, in a cell cycle nonspecific manner. Carboplatin must first undergo activation to produce antineoplastic activity. Bidentate carboxylate ligands of carboplatin are displaced by water forming (aqua) positively charged platinum complexes which bind to nucleophilic sites in DNA, such as the O-6 position on guanine. Carboplatin produces predominantly interstrand DNA crosslinks rather than DNA-protein crosslinks. Intrastrand crosslinks result from the formation of adducts between the activated platinum complexes of the drug and the N-7 atom (not exclusively) atom on guanine to produce 1,2 intrastrand links between adjacent guanine molecules, between neighboring guanine and adenosine molecules, or between neighboring guanine molecules. Interstrand cross-linking within the DNA helix also occurs.

Platinum adducts may inhibit DNA replication, transcription and ultimately cell division.

6.2.4. Carboplatin - Storage and stability

Store according to package insert recommendations

6.2.5. Carboplatin - Dose specification per protocol

Carboplatin will be IV infused at AUC 5 on D1 of each cycle, every 3 weeks. Routine premedication should include at least a 5 – HT3 antagonist and dexamethasone.

Other pre-medications, such as NK1 receptor antagonists can be given per institutional guidelines. The dose of carboplatin based on target AUC is calculated using the Calvert equation:

Dose (total mg) = Target AUC X (GFR + 25). The patient's creatinine clearance (GFR) in mL/minute is calculated by the Cockcroft Gault equation.

6.2.6. Carboplatin - Preparation

Per package insert or institutional guidelines.

Add 5, 15, or 45 mL sterile water, normal saline, or 5% dextrose to the 50, 150, or 450 mg vial, respectively. The resulting solution contains 10 mg/mL. The desired dose is further diluted, usually in 5% dextrose. Aluminum displaces platinum from the carboplatin molecule, resulting in the formation of a black precipitate and loss of potency. Carboplatin solutions should not be prepared with needles, syringes, catheters, or IV administration sets containing aluminum parts that might be in contact with the drug.

6.2.7. Carboplatin - Route of administration

Intravenous (IV) over 60 (\pm 15) minutes or per institutional guidelines

(Note: the 60 minutes duration is for Carboplatin infusion at AUC 5. If Carboplatin is given at AUC 4, then institutional standards should be followed).

6.2.8. Carboplatin - Incompatibilities

Aluminum displaces platinum from the carboplatin molecule, resulting in the formation of a black precipitate and loss of potency. Carboplatin solutions should not be prepared or administered with needles, syringes, catheters, or IV administration sets containing aluminum parts that might be in contact with the drug.

Concomitant myelosuppressive drugs or radiation therapy may potentiate the hematologic toxicity of carboplatin. Concomitant nephrotoxic drugs may potentiate the nephrotoxicity of carboplatin, particularly when carboplatin is given in high-dose chemotherapy regimens.

6.2.9. Carboplatin - Availability and Supply

Carboplatin will be given as standard of care therapy. Commercial supply of Carboplatin will be used for this study.

6.2.10. Carboplatin - Side effects

1. Hematologic: Thrombocytopenia (dose limiting), neutropenia, leukopenia, anemia.
2. GI: Nausea and vomiting (frequent but less severe than with cisplatin), treatable with appropriate antiemetic prophylaxis.
3. Anorexia, diarrhea and constipation have also been reported.
4. Dermatologic: Rash, urticaria. Rarer reactions include alopecia, mucositis, and hypersensitivity reactions.
5. Hepatic: Abnormal liver function tests, usually reversible with standard doses.
6. Neurologic: Rarely peripheral neuropathy is seen. May be more common in patients greater than 65 years of age. May also be cumulative, especially in patients with prior cisplatin treatment.
7. Ototoxicity (rare).
8. Renal: Elevations in serum creatinine, BUN; electrolyte loss (Mg, K, Na, Ca).
9. Miscellaneous: Pain, asthenia, flu-like syndrome.

6.2.11. Carboplatin - Nursing implications

1. Aluminum displaces platinum from the carboplatin molecule, resulting in the formation of a black precipitate and loss of potency. Carboplatin solutions should not be prepared with needles, syringes, catheters, or IV administration sets containing aluminum parts that might be in contact with the drug.
2. Monitor CBC and platelet count at least every 21 days or earlier if warranted per institutional standard of care.

3. Premedicate with antiemetics – prophylaxis with a 5HT3 receptor antagonist and dexamethasone (+/- aprepitant) is standard.
4. Monitor fluid status – maintain adequate hydration.
5. Assess skin/mucous membranes.
6. Assess for signs of peripheral neuropathy – coordination, sensory and hearing loss.

6.2.12. Return and Retention of Study Drug

All unused investigational products will be disposed of according to the investigational site policy for standard of care drugs.

6.2.13. Carboplatin - Toxicity Management & Dose Delays/Modifications

The dose interruption, reduction, and permanent discontinuation for any toxicity are described below.

Dose interruption: Refer to table below. Recovery to acceptable levels must occur to allow carboplatin continuation.

Table 6-4: Carboplatin Dose Modification and Management

Toxicity	Grade/Description	Carboplatin
Hematologic Toxicities		
Thrombocytopenia	Grade 1	Maintain dose level.
	Grade 2	Hold dose & follow CBC weekly. Once \leq Grade 1 (platelets \geq 75,000/mm ³), resume at same dose.
	Grade 3	Dose reduction to AUC 4
	Grade 4	Permanently discontinue Carboplatin
Neutropenia	Grade 1 , 2 or 3 without fever	Maintain dose level.
	Grade 3 w/ fever or Grade 4	1st occurrence: Hold dose & follow CBC weekly. Once resolved to $> 1.0 \times 10^9/L$ (if neutropenia was the only toxicity noted), resume at same dose. If other toxicity was noted, resume with AUC 4. 2nd occurrence: Discontinue Carboplatin
Non-Hematologic Toxicities		
Allergic reaction or hypersensitivity	\leq Grade 3	Hold dose until resolved to \leq Grade 1 & then resume at same dose level.
	Grade 4	Permanently discontinue Carboplatin

Toxicity	Grade/Description	Carboplatin
Infection	Grade 1 or 2	Hold dose until systemic treatment for infection is complete. If no neutropenia, resume at same dose level. If neutropenic, follow instructions above (hematologic section). If no resolution after > 3 weeks: permanently discontinue Carboplatin
	Grade 3	Discontinue Carboplatin
Herpes zoster or simplex	Any grade	Hold dose until lesions are dry & then resume at same dose level.
Neuropathy	Grade 2 w/pain or Grade 3	Hold dose until resolved to \leq Grade 2 or baseline then resume at AUC 4. May continue on single-agent leronlimab (PRO 140) (per treating investigator's discretion)
	Grade 4	Permanently discontinue Carboplatin
Renal dysfunction	CrCl \leq 15 mL/min	Hold dose until CrCl $>$ 15 mL/min & then resume.

Note: Patients who discontinue carboplatin for any reason will be allowed to continue to receive leronlimab (PRO 140) per treating investigator's discretion. In such cases, patients will be re-consented so that they are appropriately informed of other treatment options that have demonstrated improvement in clinical outcomes.

Dose reduction: If a dose-response relationship for toxicity is observed, a reduced dose of carboplatin AUC 4 can be given to the subject. Dose adjustments will be allowed based on the toxicity, efficacy evaluation, and clinical judgment by physician.

Permanent discontinuation: Refer to [Table 6-4](#) above.

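### In Table 6-4 carboplatin is held for Grade 2 thrombocytopenia but no hold is stated for Grade 3, and the hold for painful Grade 2 neuropathy has a release condition already met at onset

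*Protocol*

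**What the plan says.** All the operative text is in Protocol Section 6.2.13.

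- **Lead-in to the table.** Under dose interruption, the reader is sent to Table 6-4 and told: "Recovery to acceptable levels must occur to allow carboplatin continuation". No level is defined there.
- **Thrombocytopenia, Grade 2.** "Hold dose & follow CBC weekly"; carboplatin resumes at the same dose once the event is Grade 1 or better, which the cell gives as platelets of at least 75,000/mm³.
- **Thrombocytopenia, Grade 3.** The action given is "Dose reduction to AUC 4" and nothing more.
- **Thrombocytopenia, Grade 4.** "Permanently discontinue Carboplatin".
- **Neuropathy.** The trigger is "Grade 2 w/pain or Grade 3". The hold lasts until the event is at or below "Grade 2 or baseline then resume at AUC 4".
- **Text after the table.** If toxicity appears dose-related, "a reduced dose of carboplatin AUC 4 can be given to the subject", with adjustments left to toxicity, efficacy and the physician's judgment. This adds no hold and no platelet threshold for Grade 3.

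Section 6.2.11 sets the background monitoring: "Monitor CBC and platelet count at least every 21 days or earlier if warranted per institutional standard of care". It ties no weekly count to Grade 3 thrombocytopenia.

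**The concern.** A dose-modification table is normally expected to become no less cautious as the grade rises. Here the hold, the weekly count and the recovery threshold are present at Grade 2 and absent at Grade 3. Section 6.2.10 of the Protocol names thrombocytopenia as the dose-limiting hematologic effect of carboplatin, so this row is likely to matter in practice.

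In the neuropathy row, a hold is started by an event that already satisfies the grade condition for ending it.

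What is at stake is mainly patient safety and consistent conduct across up to five centers: two sites could read the same count differently and both claim to follow the protocol. There is a secondary link to the analysis. Section 11.4.1 lists an incorrect dose among its examples of major deviations, and major violations remove a subject from the Per Protocol population (Protocol Section 8.6.1.2; SAP Section 6.1.2). If the dose rule is unclear, so is that classification.

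**Working it through.** The check is mainly a comparison of rows. The one calculation is a dose ratio.

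**1. Thrombocytopenia, row by row**

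| Grade | Hold stated? | Count follow-up stated? | Recovery threshold stated? | Dose afterwards |
|---|---|---|---|---|
| 1 | No | No | Not needed | Unchanged |
| 2 | Yes | Weekly | Grade 1 or better, at least 75,000/mm³ | Same dose |
| 3 | No | No | No | AUC 4 |
| 4 | Permanent stop | – | – | None |

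The dose column falls steadily with severity. The hold column does not: it goes from no, to yes, to no, to a permanent stop.

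**2. Can a hold be read into the Grade 3 cell from the table's own style?** Other rows that want an interruption say so. The row for neutropenia at Grade 3 with fever or Grade 4 states a hold and weekly counts, then AUC 4 if another toxicity was present. The neuropathy row states a hold and then AUC 4. The rows for allergic reaction up to Grade 3, infection of Grade 1 or 2, herpes and renal dysfunction all state a hold. Section 6.2.13 also treats interruption, reduction and permanent discontinuation as three separate actions, and the Grade 3 cell uses the word for reduction.

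**3. Does the lead-in sentence settle it?** It requires recovery, gives no level, and points to the table. The Grade 3 row contains neither an interruption nor a level. Either a hold was intended and the row omits it, or none was intended and the row conflicts with the sentence. The text does not say which.

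**4. Does the question arise at a dosing decision?** It can. Protocol Section 7.11 schedules the blood count on Day 1 of each cycle, and Table 4-1, footnote 25, allows it within 3 days before the cycle starts. The count that selects the row may therefore be the pre-dose count.

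**5. Size of the dose in question.** Section 6.2.5 gives the Calvert equation, dose = AUC × (GFR + 25). For the same patient and the same GFR:

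dose at AUC 4 ÷ dose at AUC 5 = 4 × (GFR + 25) ÷ [5 × (GFR + 25)] = 4/5 = 0.80.

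The GFR term cancels, so no value need be assumed. On the literal reading, the contrast is 0% of the full dose at Grade 2 (held) against 80% at Grade 3.

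**6. Neuropathy: is the release condition true when the hold begins?** The condition is grade at or below 2, or baseline.

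- Trigger Grade 3: the grade part is false at onset. The hold ends only after improvement, so the rule works.
- Trigger Grade 2 with pain: the grade part is true at onset. Pain does not appear in the release condition, and the baseline alternative is joined by *or*, so it cannot tighten it. The hold can end as soon as it starts. The resumption at AUC 4 still applies.

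**The case against.** The strongest defense of the thrombocytopenia rows is that the lead-in sentence covers carboplatin generally and the Grade 3 cell does not cancel it. Read together, they would give recovery first and then AUC 4, with the resumed dose falling in order: same dose, AUC 4, stop. That is a natural reading, and it stands as one of two. It does not close the point, because a site following it still has no platelet level at which to resume and no schedule for checking.

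A reader might go further and infer that the protocol directs same-day AUC 4 dosing at Grade 3 counts. The documents do not support that. Literal reading of the row permits it, the lead-in argues against it, and no sentence instructs it.

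Other text also limits the risk. Counts are due at every cycle start and earlier if warranted, dose adjustment by clinical judgment is allowed, and in Phase Ib thrombocytopenia of Grade 3 or worse with bleeding is a listed event that triggers DSMB review (Protocol Sections 3 and 8.5). These safeguards are real, but none supplies the missing threshold.

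On neuropathy, a site could take resolution to mean Grade 2 without pain, since pain is what separates the trigger from ordinary Grade 2. That is sensible, but it is not what the release condition states. A reader might also infer that the whole row is without effect for painful Grade 2. That is too strong: the step to AUC 4 remains. Section 6.2.10 describes carboplatin neuropathy as rare, which bears on how often the row would be used.

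**Conclusion.** The point holds as an internal inconsistency in Table 6-4. The stated hold for thrombocytopenia is not ordered by severity, and the Grade 3 row is not reconciled with the recovery sentence above it. Read literally, a site could give 80% of the AUC 5 dose at a platelet count lower than one at which the Grade 2 row withholds treatment. In the neuropathy row the hold is empty for Grade 2 with pain only; it works for Grade 3.

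The 80% figure assumes only that the same GFR is used for both doses. The 0% versus 80% contrast depends on the literal reading of the Grade 3 cell.

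The number of patients touched cannot be estimated. The table governs all 18 + 30 = 48 planned patients, and a reader might take 48 as the number affected. It is not: only patients with Grade 3 platelets when a dose is due, or with painful Grade 2 neuropathy, meet these rows, and the documents give no incidence for either. Differences between sites in exposure or adverse event rates are possible but not shown.

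No sample size or other stated statistical figure changes. The matter should be corrected because it bears on safety and is easily put right. Nothing here implies a view on which clinical rule is correct.

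**What to change.** Reconcile the Grade 2 and Grade 3 thrombocytopenia rows with each other and with the recovery sentence above the table. The Grade 3 row should state explicitly whether a hold, count follow-up and a recovery level apply before AUC 4 is given. Reconcile the neuropathy trigger with its release condition so that the triggering event does not already satisfy it, for example by separating Grade 2 with pain from Grade 3 or by restating the release condition. The sponsor's clinical team must choose the rule in each case; none is proposed here.

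The cost is two table cells, and the lead-in sentence if needed, in the next amendment. The clarification itself requires no added patients and no change to the analysis.

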7 DESCRIPTION OF PROTOCOL ASSESSMENTS AND PROCEDURES

7.1 INFORMED CONSENT

A written informed consent will be obtained for this study for pre-screening and screening by the Investigator or designee from all subjects prior to performance of any protocol-specific procedure. This study will be conducted in accordance with the provisions of the Declaration of Helsinki.

The Investigator must comply with applicable regulatory requirements and must adhere to the Good Clinical Practice (GCP) in the process of obtaining and documenting the informed consent. The Investigator, or designee, must also inform subjects of all pertinent aspects of the study. Before written informed consent is obtained from the subject, the Investigator or a person designated by the Investigator, must provide the subject enough time and opportunity to inquire about the details of the study and to decide whether or not to participate in the trial. All questions addressed by the subject about the study must be answered to the satisfaction of the subject. Prior to the subject's participation in the trial, the written informed consent must be signed and personally dated by the subject and by the person who conducted the informed consent discussion. Authorization for release of protected health information must also be obtained, as per local policies.

7.2 ASSESSMENT OF ELIGIBILITY

The Investigator must assess subject' continued eligibility for the study as per the Inclusion and Exclusion criteria, during the Screening Period. The eligibility criteria are described in [Section 3.3.1](#) (Inclusion Criteria) and [Section 3.3.2](#) (Exclusion Criteria). In the event that the subject is not suitable or eligible for the study, the subject will be considered "screen failure".

7.2.1. Re-screening

If a subject fails initially to meet the eligibility criteria, and is later reconsidered for participation, the subject will be re-consented and assigned a new unique identification number at the time of re-screening. Subjects who fail their first screening attempt may be re-screened a maximum of once and may be enrolled in the study only if they meet all Inclusion and no Exclusion criteria when re-screened.

7.3 DEMOGRAPHIC INFORMATION AND BASELINE DISEASE CHARACTERISTICS

In this study the demographic information will include:

- Dates of ICF signature
- Date of birth
- Gender

- Race (American Indian/Alaskan Native, Asian, Black/African American, Native Hawaiian/Pacific Islander, Caucasian, or other)
- Ethnicity (Hispanic/Latino or Not Hispanic/Latino)

In addition, the following baseline disease characteristics will be collected:

- Year of initial diagnosis,
- Tumor morphology (Ductal/NOS, Lobular, Medullary, Tubular, Other, or Unknown),
- Histologic grade (I, II, III, or Unknown),
- BRCA 1/2 status,
- Menstrual status,
- Location of metastasis (Brain, Visceral, Nonvisceral)

7.4 MEDICAL HISTORY

A complete review of the subject's past medical history (including all prior anti-tumoral therapy related to breast cancer), past surgeries, and current therapies (medications and non-medications) will be undertaken by the Investigator to check that all inclusion and no exclusion criteria have been met.

Events that emerge prior to the first treatment (C1D1) will be recorded in the medical history and not as AEs. Aside from being used to determine subject eligibility, this information will permit the Investigator to record the nature, duration and severity of any ongoing baseline medical conditions prior to the subject's receiving investigational product treatment.

Medical histories will be recorded using the body system categories outlined below:

• Cardiovascular	• Lymphatic
• Respiratory	• Hematologic
• Gastrointestinal	• Immunologic
• Renal	• Dermatologic
• Hepatic	• Psychiatric
• Neurological	• Genitourinary
• Endocrine	• Other

For each relevant history, the following will be documented:

- Disease/disorder/condition

- Date of diagnosis
- History status (resolved or ongoing).

7.5 CONCOMITANT MEDICATION

The subject may be applied any medications judged necessary by the Investigator, provided such medications are not listed in [Section 7.5.2](#).

All concomitant medication administered or taken by the subject beginning 30 days prior to Screening Visit and throughout the study will be recorded in the source documents and on the appropriate page of the Case Report Form (CRF) including all prescription, over-the-counter (OTC), herbal supplements, and IV medications and fluids. If changes occur during the trial period, documentation of drug dosage, frequency, route, and date may also be included on the CRF.

Subjects must be questioned at each study visit concerning any new medications or changes in current medications including over-the-counter medication and topical medication.

For each medication and non-study treatment, the following will be documented:

- Medication/treatment name (generic name may be used if trade name is unknown)
- Dose, unit, and frequency of dosing (individual dosages, not total daily dose).
- **Note:** Each new dose of medication should be recorded as a separate entry, with the exception of medications that are given on a sliding scale. For these, it is acceptable to enter the range of the dosage, including the start and stop dates for which the specified dosage range was used.
- Route of dosing
- Indication for use
- The start date
- The stop date (if medication/therapy is not ongoing).

7.5.1. Permitted Medications

All treatments that the investigator considers necessary for a subject's welfare may be administered at the discretion of the investigator in keeping with the community standards of medical care. Patients will be permitted to receive granulocyte-colony stimulating factor (G-CSF) therapy as part of support medication for carboplatin.

7.5.2. Prohibited Medications

Subjects are prohibited from receiving the following therapies during the Screening and Treatment Period of this trial:

- Anti-cancer systemic chemotherapy or biological therapy not specified in this protocol
- Investigational agents other than leronlimab (PRO 140)
- Radiation therapy

